All events of suicidal ideation and behavior will be carefully monitored. These include events of suicide attempts, emergence or significant worsening of suicidal ideation, completed suicides, and suicidal behavior. As described in Section 8.3.5.1.1, the C-SSRS and MADRS items of the BISS, as well as the clinician's judgment, will be used in the assessment of suicidal risk by the investigator. The investigator's clinical judgment and conclusion regarding suicidal risk will be documented in the SIBQ for that visit. Clinically significant (in the opinion of the site investigator) emergence or worsening of suicidal ideation and/or behavior will be considered reportable events and documented as AEs, and a Suicidal Ideation and Behavior Reportable Event Form will be completed and submitted to medical monitor within 24 business hours of the site's knowledge of the ideation or behavior. The subject should be withdrawn from the study and the event will be adjudicated by the RAC as a potential endpoint event.

If suicidal behavior meets the criteria for a SAE, according to the guidelines in Section 12.3, investigators are required to report the event according to the guidelines for SAEs in Sections 12.3 and 12.6.1.1 and submit the completed SAE form to the medical monitor within 24

business hours. The subject should be withdrawn from the study and the event will be adjudicated by the RAC as a potential endpoint event.

The SAE Form will include the exact nature of the event and the circumstances of the subject at the time of the event, in addition to the usual information required to document AEs or SAEs. Data on all of the above will be collected on separate eCRF pages.

The latest version of the AE dictionary, MedDRA, will be used by the CRO for the classification and analysis of AEs entered in the study database. For regulatory reporting, SAEs will be processed in the Electronic Data Capture (EDC) System and coded using MedDRA.

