Worsening symptoms of the primary study condition (i.e., bipolar depression) will not be recorded as an AE. However, if inpatient hospitalization results from worsening psychiatric symptoms or suicidal ideation, the hospitalization will be recorded as an SAE in the eCRF.

Study drug abuse is an SAE, even when there are no symptoms or additional AEs, and will be reported according to the guidelines in Section 12.5. Misuse of IP is an AE, but is not considered an SAE unless accompanied by serious sequelae.

Should an overdose of study drug occur, it must be reported in accordance with the procedures described in Section 12.5. An overdose associated with symptoms must be reported as an AE, while an overdose without associated symptoms, must be reported only on the separate Clinical Study Overdose Report Form.

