Disease progression can be considered as a worsening of a subject’s condition attributable to the disease for which the study drug is being studied. It may be an increase in the severity of the disease under study and/or increases in the symptoms of the disease. The development of worsening bipolar depression will be considered as disease progression and not an AE. Events (except for suicidal ideation or behavior) which are unequivocally due to disease progression will not be reported as an AE during the study.

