13.7 Safety Endpoints

13.7.1 Overall Adverse Events

Separate safety analyses will be performed for the two stages for the Safety population. Safety endpoints will include adverse events (AE), vital signs (VS), and relevant clinical chemistries and hematology parameters.

The principle of treatment emergence will be employed for the analysis of AE data. Treatment emergence is defined to be any event that occurred during the observation period and was not present at baseline, or one which represents an exacerbation of a condition present at baseline.

Events emerging during Stage 1 will be counted during Stage 2 if not resolved by the start of randomized treatment initiation. Unresolved adverse event outcomes at the end of Stage 2 will be followed for an additional seven days or until resolution, whichever occurs earlier.

Adverse events will be classified by MedDRA. For each study treatment, safety data will be collected and analyzed per stage or until treatment-emergent adverse events are resolved. The type, incidence, timing (onset, duration), relationship, and severity of AEs will be reported for

treatment-emergent and SARs. Reasons for withdrawal due to AEs will also be reported. Narratives will be written for every AE classified as serious or associated with death. Safety results will be displayed separately for each stage and combined.

Safety and tolerability will be assessed using two-sided Fisher Exact tests to compare K/N vs. K/L and K/P. Mean changes from baseline will be displayed for each serum chemistry and hematology parameter as well as the shift; unpaired t-tests will be used to compare K/N vs. K/L and K/P; in addition, paired t-tests will be performed for the change from baseline for each study treatment group.

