13.8 Sample Size Calculations

13.8.1 Allocation

To encourage study participation, a 2:1:1 randomization will be used where at most half as many subjects will be assigned to the lurasidone and placebo arms as compared to the K/N study arm. The goal will be to have 62 subjects randomized to K/N and 31 subjects randomized to each of K/L and K/P for a total of 124 randomized subjects. The randomization takes place among Ketamine responders once confirmed by Medical Monitor.

13.8.2 Stage 1

The study goal is to achieve a total of 124 Ketamine responders for the Stage 2 evaluation. A total of 192 subjects are projected to be enrolled but this number may be reached sooner if the cumulative effect of the Ketamine response rate exceeding 70%, if the Stage 1 loss rate being less than 8% (15 subjects), or if the Stage 2 loss rate being less than 8% (9 subjects). Thus, there would be 177 subjects who complete Stage 1 before considering Ketamine response. The literature and prior experience suggests that 70% of those treated with ketamine will have an adequate reduction in depression and suicidality which equates to 124 Ketamine responders (177×0.7) who would be available for randomization. More subjects will need to be enrolled if the Ketamine response rate was lower than 70% or the randomization refusal rate was higher than 8%, considered to be part of Stage 2 losses.

13.8.3 Stage 2

Stage 2 will investigate the study hypotheses. The primary efficacy hypothesis is that K/N will delay the time to relapse relative to K/L and K/P. The goal will be to have 62 subjects randomized to K/N and 31 subjects randomized to K/L and K/P. These numbers are based on the Ketamine Responders. See **Error! Reference source not found.** for the total number of K/N and K/L subjects required to test the primary efficacy hypothesis. The sample size requirements are shown just for K/N and K/L. .

The study is powered based on the number of subjects randomized to K/N vs. K/L. In order to achieve 90% study power with two-sided 0.05 Type I error, a total of 56 K/N subjects, 28 K/L subjects, and 28 K/P subjects must be evaluated for time to relapse over the full 6 weeks. This is based on the assumption of a 30% relapse rate in the K/N treatment group and a 70% relapse rate in the K/L and K/P treatment groups. A larger gap in the relapse rate is expected based on the literature, so this is believed to be a conservative assumption. These calculations assume a loss of 8% during Stage 2.

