14.2 Audits and Inspections

Subcontracts with study sites will specify that sponsor or its representatives will have direct access to source data and documents for study monitoring. Additionally, the IRB and FDA may review source data following appropriate guidelines for this process.

The Data and Safety Monitoring Board (DSMB) functions include, among others, ongoing assessment of masked data to determine whether any of the treatment arms show increased risk for AEs. The main purpose of the DSMB is to assess safety of the intervention by determining whether an increased number of AEs are occurring among study participants in any one of the treatment groups. Data will be reviewed every 4 months after the DSMB approval of the DSMB Charter. Frequent interim review of the data for SAEs does not require statistical adjustment for repeated testing or analyses.

The Medical Monitor for this trial will be designated by sponsor/CRO. The Medical Monitor will review and approve the eligibility of all screened subjects, review all AEs, assess the benefits and risks of protocols on an ongoing basis, and work in collaboration with the IRB and RAC to identify safety signals and trends.

In addition, the Medical Monitor will be available for site questions. The Medical Monitor will be available to sites for questions regarding inclusion/exclusion criteria, protocol conduct, and safety. Trained and qualified physicians will be available to provide coverage during times when the medical monitor is unavailable. Sites will be provided with the Medical Monitor's cell phone number for emergency situations. Otherwise, sites are instructed to contact the Medical Monitor through email. All conversations with sites will be documented by the Medical Monitor and reviewed periodically by the sponsor.

Each month the Medical Monitor will receive a listing of protocol violations for review and identification of possible trends.

Serious adverse events will be reported to the CRO by the site within 24 business hours of the site's knowledge of the event. For reportable unexpected and/or related SAEs, the Medical Monitor will contact NeuroRx within 48 business hours of the notice by the site. In addition, the

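### Suicidality and psychiatric admissions count both as adverse events and as candidate relapses, and no between-arm AE or SAE comparison separates the two

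*Combined protocol and SAP*

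**What the plan says.** **Recording.** Section 12.1 provides that, where the site investigator judges it clinically significant, "emergence or worsening of suicidal ideation and/or behavior will be considered reportable events and documented as AEs". It continues: "The subject should be withdrawn from the study and the event will be adjudicated by the RAC as a potential endpoint event". Section 12.3 adds that "if inpatient hospitalization results from worsening psychiatric symptoms or suicidal ideation, the hospitalization will be recorded as an SAE in the eCRF". The disease-progression exclusion in 12.5 does not reach suicidality: "Events (except for suicidal ideation or behavior) which are unequivocally due to disease progression will not be reported as an AE during the study". Worsening depression alone is treated differently. Section 12.3 says "Worsening symptoms of the primary study condition (i.e., bipolar depression) will not be recorded as an AE".

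**Endpoint.** Section 8.2.5.1.1 defines relapse as a C-SSRS of 4 or more, a MADRS-subset score of 20 or more, or a physician-judged change of treatment plan, with re-hospitalization as an example. The first and third components can be the same events that 12.1 and 12.3 record as AEs or SAEs.

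**Use.** Sections 8.2.5.2.1 and 13.7.1 state: "Safety and tolerability will be assessed using two-sided Fisher Exact tests to compare K/N vs. K/L and K/P". Section 13.10.8 also compares overall incidence by Fisher test. Section 14.2 gives the DSMB's main purpose as "determining whether an increased number of AEs are occurring among study participants in any one of the treatment groups". Section 9.4 lets the DSMB request a code break for an imbalance in safety parameters.

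**Expected relapse.** Section 13.8.3 assumes a "30% relapse rate in the K/N treatment group and a 70% relapse rate in the K/L and K/P treatment groups".

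**The concern.** One event can enter the primary efficacy endpoint and the safety comparison, and nothing in sections 12 to 14 separates the two uses. If NRX-101 prevents relapse, the comparator arms collect more suicidality AEs and psychiatric SAEs for that reason alone. A real excess of other AEs on NRX-101 can be offset in the pooled count, or equal tolerability can look like a safety benefit that is really efficacy.

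This matters more than usual because 8.2.5.2.3 notes that only 21 subjects have received 1000 mg of d-cycloserine in formal psychiatric studies. A DSMB trigger based on imbalance between arms is exposed to the same offset.

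**Working it through.** **1. The plan's own figure.** The hazard ratio is ln(0.30)/ln(0.70) = 3.376, as in Table 12. Freedman's formula at two-sided 0.05 and 90% power gives (1.960 + 1.282)² × (4.376/2.376)² = 35.6, so 36 events. With 56 K/N and 28 K/L subjects, expected events are 56 × 0.30 + 28 × 0.70 = 36.4. The evaluable sizes therefore match the relapse rates in the text of 13.8.3. Table 12's 90% column carries 52% relapse-free for K/N instead. I use the rates in the text. At 48% relapse on K/N the offset below would be smaller.

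**2. Expected relapses as randomized (62:31:31).** K/N: 62 × 0.30 = 18.6. Each comparator: 31 × 0.70 = 21.7.

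**3. Pooled incidence.** Let t be the incidence of other AEs, r the relapse rate and f the share of relapses logged as AEs. Neither t nor f is in the documents, so both are assumptions. Taking other AEs as independent of relapse:

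any-AE incidence = 1 − (1 − t)(1 − f·r)

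Power is for the exact two-sided Fisher test at 0.05, 62 versus 31, by full enumeration. With t = 60% on K/N and 30% on a comparator:

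| f | K/N | Comparator | Gap (points) | Power |
|---|---|---|---|---|
| 0 | 60.0% | 30.0% | 30.0 | 79% |
| 10% | 61.2% | 34.9% | 26.3 | 67% |
| 25% | 63.0% | 42.3% | 20.8 | 47% |
| 50% | 66.0% | 54.5% | 11.5 | 17% |
| 75% | 69.0% | 66.8% | 2.3 | 4% |

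For example, at f = 50%: K/N is 1 − 0.40 × 0.85 = 66.0% and the comparator is 1 − 0.70 × 0.65 = 54.5%.

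**4. Apparent advantage.** With t = 20% in both arms and f = 50%, incidence is 1 − 0.80 × 0.85 = 32% versus 1 − 0.80 × 0.65 = 48%. Fisher finds the comparator significantly worse in 30% of trials, against 2% with no overlap.

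**5. SAEs.** Assume other SAEs of 10% versus 2%. If 10% of relapses lead to admission, the rates become 1 − 0.90 × 0.97 = 12.7% versus 1 − 0.98 × 0.93 = 8.9%, so K/N still looks worse. If half do, they become 1 − 0.90 × 0.85 = 23.5% versus 1 − 0.98 × 0.65 = 36.3%, and the sign reverses.

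**6. The opposing effect.** Relapsers are withdrawn (8.1 and 12.1), so the comparator arms have less exposure. Suppose the other-AE hazard is equal in all arms, λ = −ln(0.40) = 0.916 over six weeks. Let the relapse hazards be constant, μ = −ln(0.70) = 0.357 on K/N and −ln(0.30) = 1.204 on a comparator, and let AE counting stop at withdrawal. Crude incidence is then λ/(λ + μ) × [1 − exp(−(λ + μ))]:

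- K/N: 0.720 × 0.720 = 52%
- Comparator: 0.432 × 0.880 = 38%

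That is 14 points against NRX-101 with no true difference.

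**The case against.** The strongest case against has five parts.

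- **The overlap is partial.** Worsening depression without admission is not an AE, so MADRS-only relapses and plan changes without suicidality or admission stay out. Suicidality counts only if the investigator finds it clinically significant. Section 8.1 expects subjects enrolled at C-SSRS level 4 mostly to be managed as outpatients, which may keep admissions low. This stands: f is below 100% and could be small.
- **One pooled test is partly inferred.** AEs are also reported by type, relationship and severity. In 13.10.8 the overall-incidence sentence follows planned surveillance findings. PRISE, BARS, ECG and laboratory comparisons lie outside AE counts. This stands in part: toxicity could still be seen there, but none of it changes a pooled Fisher comparison or a total AE count.
- **Some separation exists.** Section 12.4 rates deterioration from lack of effect as having no reasonable possibility of drug causation. That changes only the causality rating, and neither the Fisher tests nor the DSMB counts are limited to related events. Suicide rates and disease-related hospitalizations and ER visits have their own analyses (13.10.7), but they are not removed from AE totals.
- **The DSMB charter is not in the documents** and may already split these events.
- **Excluding relapses can itself hide toxicity.** A drug-induced psychiatric reaction that leads to admission might be reported as relapse, and suicidality is a safety outcome in its own right. This stands and shapes the fix.

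A reader might infer that the plan is biased in NRX-101's favour or will conceal its toxicity. The documents do not support that: the overlap share is unknown, and shorter comparator exposure works in the opposite direction.

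**Conclusion.** The point holds as a gap in the safety analysis. Certain events are both AEs or SAEs and candidate relapses, and the stated between-arm comparisons do not distinguish them. At the planned 30% versus 70% relapse, pooled incidence partly reflects efficacy and can mask an NRX-101 excess or suggest a safety advantage.

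The size is conditional. At assumed other-AE rates of 60% versus 30%, independent of relapse, the loss of power runs from 12 points (79% to 67%) at 10% overlap to 75 points (79% to 4%) at 75% overlap. The documents do not say where in that range the trial would fall, and withdrawal of relapsers may offset or reverse the effect on crude incidence. The supported conclusion is that crude pooled rates cannot be read as tolerability alone. They do not show in which direction the rates will mislead. This is a low-cost improvement to the plan.

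**What to change.** Keep all AE and SAE recording and reporting, and keep the all-event K/N versus K/L and K/N versus K/P comparisons. In 13.7.1, 13.10.8 and the DSMB tables, add:

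1. The same AE and SAE comparisons excluding only events the RAC has confirmed as relapse. Events merely reported to the RAC stay in, so that drug-induced psychiatric toxicity is not removed on a site's provisional label.
2. Suicidality and psychiatric admissions as their own category, by arm.
3. Exposure-adjusted AE and SAE rates, because relapsers are withdrawn and follow-up will differ between arms.

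The cost is one flag linking AE records to RAC results and one extra set of tables. RAC determinations already go into the study database (8.2.8) and suicidality data are already on separate eCRF pages (12.1), so no new data collection is needed. The downside is that the two sets of tables must be read together. The RAC meets monthly, so the separated DSMB tables may lag slightly behind the all-event ones.

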12.2 Definition of Adverse Events

An adverse event (AE) is any untoward medical occurrence in a clinical study subject administered a medicinal (investigational or non-investigational) product. An AE does not necessarily have a causal relationship with the treatment. An AE can therefore be any unfavorable and unintended sign (including an abnormal finding), symptom, or disease temporally associated with the use of a medicinal (investigational or non-investigational) product, whether or not related to that medicinal (investigational or non-investigational) product. (Definition per ICH).

This definition includes any occurrence that is new in onset or aggravated in severity or frequency from the baseline condition, or abnormal results of diagnostic procedures, including laboratory test abnormalities.

The following variables will be collected for each AE:

- AE (verbatim)
- The date and time when the AE started and stopped
- Maximum intensity or intensity or changes in intensity
- Whether the AE is serious or not
- Expectedness
- Investigator causality rating against study drug (yes or no)
- Action taken with regard to the Investigational Product (IP)

- AE caused subject's withdrawal from the study (yes or no)
- Outcome

Any AEs that are unresolved at the subject's last AE assessment in the study are followed up by the investigator for as long as medically indicated, but without further recording in the eCRF. MGH CTNI or its representative retains the right to request additional information for any subject with ongoing AE(s)/SAE(s) at the end of the study, if judged necessary.

12.3 Definition of Serious Adverse Events

The following criteria define a Serious Adverse Event:

- Death
- Life-threatening event
- Inpatient hospitalization >24 hours or
- Prolongation >24 hours of inpatient hospitalization
- Persistent or significant disability/incapacity
- Congenital anomaly/birth defect
- Medically important event, as defined in this protocol*

*Medical and scientific judgment will be exercised in deciding whether expedited reporting is also appropriate in other situations, such as important medical events that may not be immediately life threatening or result in death or hospitalization but may jeopardize the subject or may require intervention to prevent one of the other outcomes listed in the definition above. These will usually be considered serious.

If a serious and unexpected AE occurs for which there is evidence suggesting a causal relationship between the study drug and the event (e.g., death from anaphylaxis), the event must be reported as a serious and unexpected suspected adverse reaction even if it is a component of the study endpoint (e.g., all-cause mortality).

In addition, the following variables will be collected for SAEs:

- Date AE met criteria for SAE
- Date investigator became aware of SAE
- AE is serious due to
- Date of hospitalization
- Date of discharge
- Probable cause of death

- Date of death
- Autopsy performed
- Causality assessment in relation to study procedure(s)
- Causality assessment in relation to study drug
- Causality assessment in relation to other medication
- Description of AE

Intensities will be reported for each AE in the following categories: a) Mild (awareness of sign or symptom, but easily tolerated); b) Moderate (discomfort sufficient to cause interference with normal activities); c) Severe (incapacitating, with inability to perform normal activities).

It is important to distinguish between serious and severe AEs. Severity is a measure of intensity whereas seriousness is defined by these criteria. An AE of severe intensity need not necessarily be considered serious. For example, nausea that persists for several hours may be considered severe nausea, but not an SAE. On the other hand, a stroke that results in only a limited degree of disability may be considered a mild stroke, but would be an SAE.

Worsening symptoms of the primary study condition (i.e., bipolar depression) will not be recorded as an AE. However, if inpatient hospitalization results from worsening psychiatric symptoms or suicidal ideation, the hospitalization will be recorded as an SAE in the eCRF.

Study drug abuse is an SAE, even when there are no symptoms or additional AEs, and will be reported according to the guidelines in Section 12.5. Misuse of IP is an AE, but is not considered an SAE unless accompanied by serious sequelae.

Should an overdose of study drug occur, it must be reported in accordance with the procedures described in Section 12.5. An overdose associated with symptoms must be reported as an AE, while an overdose without associated symptoms, must be reported only on the separate Clinical Study Overdose Report Form.

12.4 Relationship to Study Drugs

Adverse events and SAEs will be collected from the time of signature of informed consent throughout the treatment period. Unsolicited SAEs will be collected 30 days post last study treatment.

The investigator will assess the causal relationship (i.e., the relationship to study treatment) between the IP and AEs, and answer “yes” or “no” to the question “Do you consider that there is a reasonable possibility that the event may have been caused by the investigational product?” Causal relationship in cases where the depression or suicidal ideation has deteriorated due to lack of effect will be classified as no reasonable possibility. For SAEs, causal relationship will also be assessed. Note that for SAEs that could be associated with any study procedure, the causal relationship is implied as “yes.”

An AE is considered unexpected if it is not listed in the IB, or the nature or severity is not consistent with the applicable reference in the IB.

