4.6 Investigational Therapy

The investigational therapy to be evaluated in this study consists of sequential treatment consisting of the following components:

1. an initial, one-time intravenous infusion of ketamine (0.5 mg/kg administered over 40 min) on Day 0, followed by
2. twice daily oral capsules of NRX 101 (d-cycloserine [DCS] + lurasidone), which is initiated on Day 1 (in subjects who respond to ketamine) and continued for up to 6 weeks. It is anticipated that subjects entering the study will be receiving concurrent disorder-directed treatment with various predefined combinations of medications. This treatment regime will be maintained upon entry into the study. However, any use of lurasidone, quetiapine, or olanzapine will be stopped at study entry. This regimen may be supplemented with mood stabilizers at the discretion of the treating physician.

Our clinical objective is to offer patients the clinical benefit of rapid reduction in symptoms of depression and suicidal ideation that has been observed with intravenous ketamine, while maintaining that benefit with a daily oral agent that does not have ketamine's potential for abuse and psychosis.

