8.2.5.2 Safety Endpoints

8.2.5.2.1. Overall Adverse Events

Separate safety analyses will be performed for the two stages for the Safety population. Safety endpoints will include adverse events (AE), vital signs, and relevant clinical chemistries and hematology parameters.

The principle of treatment emergence will be employed for the analysis of AE data. Treatment emergence is defined to be any event that occurred during the observation period and was not present at baseline, or one which represents an exacerbation of a condition present at baseline.

Events emerging during ketamine treatment will be counted during the randomized phase of the study if not resolved by the start of randomized treatment initiation. Unresolved AE outcomes at the end of randomized treatment will be followed for an additional seven days or until resolution, whichever occurs earlier.

Adverse events will be classified by MedDRA. For each study treatment, safety data will be collected and analyzed per stage or until treatment-emergent AEs are resolved. The type, incidence, timing (onset, duration), relationship, and severity of AEs will be reported for treatment-emergent and suspected adverse reactions. Reasons for withdrawal due to AEs will also be reported. Narratives will be written for every AE classified as serious or associated with death. Safety results will be displayed separately for each stage and combined.

Safety and tolerability will be assessed using two-sided Fisher Exact tests to compare K/N vs. K/L and K/P. Mean changes from baseline will be displayed for each serum chemistry and hematology parameter as well as the shift; unpaired t-tests will be used to compare K/N vs. K/L and K/P; in addition, paired t-tests will be performed for the changes from baseline for each study treatment group.

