10. STUDY DRUG MATERIALS AND MANAGEMENT

10.1 Study Drugs

Ketalar (ketamine hydrochloride injection) will be purchased from PAR Sterile Products, [name]. It will be provided as IV infusion administration.

The Investigational Product (IP) is a capsule intended for oral administration. Each capsule contains DCS and lurasidone hydrochloride. Inactive ingredients include mannitol, croscarmellose sodium, silica dioxide, and magnesium stearate.

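### The causality rating has no consistent object (ketamine, capsule or either) and two scales, so the planned Stage 1 relationship results cannot be interpreted

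*Combined protocol and SAP*

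**What the plan says.** All references are to the combined protocol and SAP.

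- **The question put to investigators (12.4).** Adverse events are collected from consent through the treatment period. "The investigator will assess the causal relationship (i.e., the relationship to study treatment) between the IP and AEs", and the question to be answered yes or no is "Do you consider that there is a reasonable possibility that the event may have been caused by the investigational product".
- **What the investigational product is (10.1).** "The Investigational Product (IP) is a capsule intended for oral administration". The synopsis and Table 11 likewise give NRX-101 as the investigational product. Ketamine appears separately, but under the same Study Drugs heading: "Ketalar (ketamine hydrochloride injection) will be purchased from PAR Sterile Products".
- **What the therapy is (4.6).** "The investigational therapy to be evaluated in this study consists of sequential treatment consisting of the following components". The first component listed is the ketamine infusion; the second is the capsule, started on Day 1 in responders.
- **What is collected for each event (12.2).** "Investigator causality rating against study drug (yes or no".
- **What else is collected for serious events (12.3).** "Causality assessment in relation to study procedure(s", with further items for study drug and for other medication.
- **What the CRF must hold (12.6).** The investigator's opinion on relationship to study therapy, for all adverse events.
- **A second scale (12.6.1.1).** Relationship to test drug is part of the event description. Events are then coded unrelated, unlikely, possible or probable, and the last two count as related to study medication.
- **What is reported (8.2.5.2.1, repeated in 13.7.1).** "Separate safety analyses will be performed for the two stages for the Safety population". Relationship is among the listed outputs, shown by stage and combined. Stage 1 events unresolved when randomised treatment starts are also counted in Stage 2. Section 13.10.8 again lists relationship.

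**The concern.** A relationship table is only as good as the question behind it. In Stage 1 the only treatment is ketamine, but the one question actually worded for investigators is about a capsule that nobody has yet taken. Other sections invite a rating against something wider. Sites can follow the protocol correctly and still answer different questions, and the data will not show which question was answered.

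At stake is the descriptive safety account of the infusion, which is given to every subject and is the first component of the therapy under study. A smaller issue arises early in Stage 2. The capsule starts about 24 hours after the infusion, so an event that begins soon after the first capsule could reasonably be attributed to either agent, and a single rating does not record which. The investigator's judgement of the agent cannot be reliably reconstructed afterwards.

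**Working it through.** No stated statistic is in dispute. The check compares the causality passages, with one subtraction for scale.

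**Step 1. Object and scale of the rating, section by section.**

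| Section | Object of the rating | Scale | Applies to | Covers ketamine? |
|---|---|---|---|---|
| 12.4, question | investigational product | yes/no | AEs from consent | No, by the 10.1 definition |
| 12.4, lead-in sentence | study treatment, equated with IP | – | same | Unclear; 13.10.8 speaks of Stage 1 treatment |
| 12.2 | study drug | yes/no | every AE | Yes, if read with the 10.1 heading |
| 12.6 | study therapy | not stated | every AE | Yes, if read with 4.6 |
| 12.6.1.1 | test drug, then study medication | four levels | every AE | Not stated |
| 12.3 | study procedure, study drug, other medication | not stated | SAEs only | Yes, but the item that holds ketamine is not named |

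No section says whether the rating means ketamine, the capsule or either. None says which scale feeds the tables. The probable category in 12.6.1.1 also refers to the investigational medicinal product and relies on improvement on cessation and return on rechallenge, which are hard to apply to a one-time infusion.

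**Step 2. Apply this to a Stage 1 event.** Take a non-serious event that starts after the infusion and before any capsule. Under the literal 12.4 question the answer is no, because the capsule has not been taken. Under 12.2 or 12.6 the answer may be yes, because ketamine is a study drug and part of the therapy. Both answers comply with the protocol.

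**Step 3. Apply this to Stage 2.** Event start and stop dates and times are collected (12.2), as are infusion start and stop times (8.1.4) and capsule dosing dates and times (9.2).
- Onset before the first capsule: the event can be identified by timing, even when it is carried into the Stage 2 tables.
- Onset after the first capsule: timing alone does not settle the agent. A non-serious event has one causality item, so the judgement on the agent is lost.

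**Step 4. Scale, from 13.8.2 and Table 12.** Inputs are 192 enrolled, 8% Stage 1 losses (15 subjects), 70% ketamine response and 124 randomised.
- Completing Stage 1: 192 − 15 = 177, as the plan states.
- Responders: 177 × 0.70 = 123.9, or about 124, as the plan states.
- Infused but never given a capsule, if all Stage 1 losses precede infusion: 177 − 124 = 53 (53/177 = 30% of those infused).
- The same, if all Stage 1 losses follow infusion: 192 − 124 = 68 (68/192 = 35%).

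The Stage 1 events of the other 124 subjects raise the same ambiguity. The documents give no expected event counts, so the number of affected events cannot be estimated.

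**The case against.** The strongest reply is that this is loose terminology and not a gap in the data. The 12.4 heading refers to study drugs in the plural, and its lead-in sentence explains the rating as relationship to study treatment. Sections 12.2 and 12.6 require a rating for every event in terms that can include ketamine. Serious events have extra causality items, and 12.4 implies yes for those that could be associated with a study procedure. Stage 1 has one arm and one drug, and its acute effects are also captured by the CADSS, BPRS, PRISE and vital signs. Every arm received the same open-label ketamine before blinded randomisation, so attribution to ketamine should not differ by arm. The planned arm comparisons use Fisher tests and Poisson counts, and none is specified as restricted to related events.

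Much of this stands. It rules out two inferences a reader might draw from 12.4 and 10.1 alone. The first is that no ketamine-stage event can be rated related, so that the Stage 1 table must show 0 among 192 subjects. The documents do not support this, because 12.2, 12.6 and 12.6.1.1 allow a wider rating; in addition, 192 is the number enrolled, not the number infused. The second is that ketamine and capsule events cannot be told apart at all in Stage 2. Onset times separate those that began before the first capsule.

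The reply does not supply a single object for the rating. The wider terms show that sites may answer differently; they do not say which answer is wanted. The separate items in 12.3 are for serious events only.

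**Conclusion.** The point holds as an inconsistency in what is collected, not as a demonstrated error in any result. The Stage 1 relationship output cannot be interpreted as planned, because compliant sites may rate against the capsule, against ketamine or against either, on one of two scales. For non-serious events starting soon after the first capsule, the agent judged causal is not recorded. About 53 to 68 subjects would have ketamine exposure only, and the pre-capsule events of the randomised subjects are affected too.

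Overall adverse event incidence, the planned between-arm tests and the efficacy analyses are not affected. In Stage 2 the effect is blurring of a descriptive table, with no reason to expect it to favour one arm.

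Assumptions: the plan's 8% loss and 70% response rates hold; all 124 randomised subjects take at least one capsule (13.8.2 counts refusals of randomisation among Stage 2 losses, so the range could be slightly higher); and the eCRF and its completion instructions, which are not in the documents, do not already settle the object of the rating.

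**What to change.** In 12.2, 12.4, 12.6, 12.6.1.1 and the eCRF:

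1. Record causality for every adverse event against ketamine and, from the first capsule on, separately against the blinded capsule.
2. Use one term for each agent throughout, and say which 12.3 item holds ketamine for serious events.
3. Choose one scale, yes/no or four-level, and name it as the source for the tables.
4. In 8.2.5.2.1, 13.7.1 and 13.10.8, tabulate Stage 1 relationship against ketamine, and Stage 2 relationship against the capsule with the ketamine rating beside it.

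The cost is aligned wording, an added causality item and slightly more data entry per event. Sample size, randomisation, blinding and treatment are untouched.
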